**Table 6-8      Clinically relevant drug interactions: inducers, and inhibitors of isoenzyme CYP3A**

Inducers
carbamazepine, glucocorticoids, modafinil, oxcarbazepine, phenobarbital, phenytoin, pioglitazone, rifabutin, rifampin, St. John's wort, troglitazone, efavirenz, nevirapine, topiramate, avasimibe, bosentan, etravirine, nafcillin, ritonavir, talviraline (not available in US market), tipranavir, amprenavir, aprepitant, armodafinil (R-modafinil), dexamethasone, nevirapine, prednisone, pleconaril (not available in US market), rufinamide
Inhibitors
Strong inhibitors: clarithromycin, conivaptan, indinavir, itraconazole, ketoconazole, lopinavir, mibefradil, nefazodone, nefinavir, ritonavir, saquinavir, telithromycin, troleandomycin, voriconazole, tipranavir, elvitegravir, Posaconazole ( Krishna et al 2009 )
Moderate inhibitors: aprepitant, atazanavir, casopitant, cimetidine, ciprofloxacin, darunavir, diltiazem, erythromycin, fluconazole, grapefruit juice (citrus parasida fruit juice), imatinib, tofisopam, verapamil, amprenavir, fosamprenavir, dronedarone

**Table 6-9 Clinically relevant drug interactions: substrates, inducers, inhibitors of PgP and PgP/CYP3A dual inhibitors**

Substrates
digoxin, fexofenadine, indinavir, vincristine, colchicine, topotecan, paclitaxel
Inducers
rifampin, St John's wort
PgP Inhibitors and PgP/CYP3A Dual Inhibitors
amiodarone, captopril, carvedilol, clarithromycin, conivaptan, diltiazem, dronedarone, elacridar, erythromycin, felodipine, fexofenadine, ginkgo (ginkgo biloba), indinavir, itraconazole, , lopinavir, mibepradil, milk thistle (silybum marianum), nifedipine, nitrendipine, quercetin, quinidine, ranolazine, ritonavir, saquinavir, Schisandra chinensis, St John's wort (hypericum perforatum), talinolol, telmisartan, tipranavir, valspar, verapamil
Reference: Internal Clinical Pharmacology Drug-drug interaction (DDI) memo, updated Oct. 2, 2011, which summarizes DDI data from three sources including the FDA's "Guidance for Industry, Drug Interaction Studies", the University of Washington's Drug Interaction Database, and Indiana University School of Medicine's Drug Interaction Table.

## Vaccinations

Immunosuppressants may affect the response to vaccination and vaccination during treatment with everolimus may therefore be less effective. The use of live vaccines should be avoided during treatment with everolimus. Examples of live vaccines are: intranasal influenza, measles, mumps, rubella, oral polio, BCG, yellow fever, varicella, and TY21a typhoid vaccines.

### 6.3.2 Prohibited concomitant therapy

None.

## 7 Visit schedule and assessments

### 7.1 Study flow and visit schedule

#### 7.1.1 Screening assessments

Written informed consent must be obtained and documented in the medical record before starting protocol therapy. After receiving a subject's agreement to participate in the study and verifying that the subject eligibility criteria, the study site will begin further pretreatment evaluation as follows:

- Clinical Evaluation: A complete history and neurological examination (including assessment of Karnofsky Performance Status [Appendix 1], vital signs [height, weight, blood pressure, pulse, respiration rate, temperature and pulse oximetry], physical and neurologic examination) is to be done within 14 days of initial protocol treatment.

- Radiographic Evaluation: An MRI scan must be performed within 28 days prior to initial treatment on a dose of steroids that has been stable or decreasing for 5 days or more. MR spectroscopy are optional.
- Laboratory Evaluation: Blood tests may be performed at the UCSF clinical laboratory, or at a local laboratory. Pre-study laboratory tests must be obtained with 14 days prior to initial protocol treatment except as noted below. Pre-study laboratory tests shall include:
  - CBC, platelets, differential, PT (INR)
  - Sodium, potassium, chloride, bicarbonate, calcium, fasting glucose, albumin, total protein, BUN, serum creatinine
  - T. bilirubin, AST, ALT, alkaline phosphatase, phosphorus,
  - Fasting serum lipid profile (total cholesterol, triglycerides, HDL and LDL)
  - Serum pregnancy test for women of childbearing potential (performed within 7 days of initial protocol treatment).
  - Hepatitis B/C testing: Patients will be tested for the following hepatitis serologic markers: HBsAg, HBs Ab, HBC Ab Total, and HCV antibodies (performed within 28 days of initial protocol treatment).
- Electrocardiogram (ECG): A standard 12 lead ECG is to be performed within 14 days of initial protocol treatment and significant findings must be recorded.
- Tumor tissue testing for treatment selection, as per Section 7.3.2
- Research blood sample (if needed): If blood has not already been collected for a patient in the BTRC Tissue Bank, then one tube of blood will be drawn to serve as a comparison for correlative tissue studies described in Appendix 2, Section C.
- Quality of Life Surveys (optional): 2 surveys will be completed during the screening period at UCSF. The surveys will ask patients about his/her feelings, beliefs and behaviors before beginning treatment.

### 7.1.2 Assessments During Treatment

- A cycle will be 28 days in length regardless of treatment delays; in particular, for patients also receiving temozolomide, if there is a delay in re-initiating temozolomide, Day 1 of that cycle will not shift with the temozolomide.
- At the end of cycle 1 (Day 28, +/- 7 days), a toxicity check will be performed via telephone call.

- Clinical Evaluation: Clinical assessments will be required every 2 cycles for the first 12 cycles, then every 3 cycles for the next 12 cycles. Whenever possible, all assessments at each scheduled time-point will be completed in a single clinic visit. Clinical assessments performed at required visits will include the following:
  - Karnofsky performance status (Appendix 1)
  - Neurologic Examination (see below)
  - Physical Examination
  - Pulse Oximetry measurements
  - Vital Signs: pulse, blood pressure, respiration rate, temperature and weight.
  - A Neuro Exam Score should be recorded at each patient visit according to the following scale (compared to baseline, defined as neurologic exam at time of screening).

+2	Definitely better
+1	Possibly better
0	Unchanged
-1	Possibly worse
-2	Definitely worse
- Radiographic Evaluation: An MRI will be required every 2 cycles for 12 cycles, and every 3 months for the subsequent 12 cycles. MR spectroscopy scans are optional, and will be done at the following timepoints: baseline, at the end of cycles 2 and 6, and at the time of tumor progression.
  - Imaging Score: This will be recorded every time a patient has an imaging study.

+3	Disappearance of tumor (CR)
+2	Definitely better (PR)
+1	Possibly better
0	Unchanged
-1	Possibly worse
-2	Definitely worse (PD)
-3	Development of a new lesion (PD)
- Laboratory Evaluation:
  - **Arms 1 and 3** (everolimus alone):
    - CBC, platelets, differential (Day 28 (+/- 7 days) of each cycle)

- **Arm 2** (everolimus and temozolomide)
  - CBC, platelets, differential (Days 21 (+/- 3 days) and 28 (+/- 3 days) after the first dose of temozolomide while on temozolomide and everolimus, then Day 28 (+/- 7 days) when on everolimus alone.)
- **All Arms:**
  - Sodium, potassium, chloride, bicarbonate, calcium, fasting glucose, albumin, total protein, BUN, serum creatinine (Day 28 (+/- 7 days) of each cycle)
  - T. Bilirubin, AST, ALT, alkaline phosphatase, phosphorus (Day 28 (+/- 7 days) of each cycle)
  - Fasting serum lipid profile (total cholesterol, triglycerides, HDL and LDL) (Day 28 (+/- 7 days) of each even cycle for first 12 cycles, then Day 28 (+/- 7 days) of every 3rd cycle thereafter)
  - Serum pregnancy test: for women of childbearing potential (Day 28 (+/- 7 days) of each cycle).
  - Note the coadministration of everolimus and oral anticoagulants is possible but should be subject to verification of coagulation (INR) once steady state is reached (after one week's treatment).

\*The intent is for these tests to be checked approximately every 28 days for all patients, regardless of treatment delays due to myelosuppression.

- Documentation: All relevant information regarding drug doses, concomitant medications and doses, evaluable lesions with measurements, tumor response, laboratory examinations, and treatment-related toxicities shall be documented in the patient's medical record and flow sheets. Patients will maintain a treatment diary while on therapy. The treatment diary will be initiated on Day 1 of therapy and continue throughout treatment. Treatment diaries will be collected from the patient every 2 cycles for the first 12 months, then every 3 cycles until the patient discontinues therapy.
- Treatment or visit delays for public holidays or weather conditions do not constitute a protocol violation.
- Quality of Life Surveys (optional): 2 surveys will be completed at the end of every 6 cycles while on treatment, (if possible) prior to tumor assessment discussion with the physician.

### 7.1.3 Follow-up Assessments

- Protocol Completion Assessment:

- After administration of everolimus for two years, patients will have completed study treatment.
- All patients must be observed for safety for 30 days following the last dose of everolimus prior to withdrawal from study. This defines completion of active study participation.
- Physical examination and comprehensive neurologic examination and grading, vital signs including weight, Karnofsky Performance status, all laboratory values, and MRI of the brain must be repeated within 4 weeks of the last day of study only if these have not been evaluated within 14 days, inclusive, prior to the date of withdrawal from study, if patients are able to return to do so. If patients are unable to return for an in-person visit, then they will be contacted by phone to assess toxicity at approximately 4 weeks after that last day of study.
- Quality of Life Surveys (optional): 2 surveys will be completed 1 year post-completion of treatment or at the time of tumor progression if sooner than 1 year post-completion of treatment.
- Long-term Follow-up:
  - After completion of study treatment, patients whose tumors have not progressed will be followed with interval MRIs. These should be done every 4 months (+/- 2 weeks) for 1 year, then every 6 months (+/- 4 weeks) for an additional 2 years, and thereafter as per the discretion of the managing physician.
  - Patients will be followed according to routine clinical practice after removal from protocol therapy or until death, whichever occurs first.
  - Patients removed from protocol therapy for unacceptable adverse events will be followed until resolution or stabilization of the adverse event.
  - Patients off protocol therapy will continue to be followed for PFS and OS only for the purposes of this protocol. If patients are not being seen regularly in clinic, then phone calls for PFS and OS will be made every 6 months.

**Table 7-1** Visit evaluation schedule (note: 1 cycle = 28 days)

Procedures:	Initial Screen	1-month Assessment (by phone)	Assessments every 2 cycles (+/- 7 days unless otherwise noted) for cycles 1-12 of therapy	Assessments every 3 cycles (+/- 7 days unless otherwise noted) for cycles 13-24 of therapy	28 days after completing protocol therapy (+/- 7 days) †	Long Term Follow-Up
Clinical Evaluation: ‡						
Medical History	X					
Vital Signs and KPS ¥	X		X	X	X	
Physical Exam, Neurologic Exam	X		X	X	X	
Toxicity Check	X £	X	X	X	X	
Pulse Oximetry	X		X	X	X	
ECG	X					
QoL questionnaires	X		X §			
Laboratory/ Diagnostic Tests: ‡						
Serum pregnancy for women of child-bearing potential	X	Day 28 (+/- 7 days) while on therapy			X	
CBC with diff and platelets*	X	Arms 1 and 3: Day 28 (+/- 7 days) while on therapy Arm 2: Day 21 (+/- 3 days) and day 28 (+/- 3 days) from 1 st day of temozolomide treatment while on dual therapy with both drugs, then Day 28 (+/- 7 days) while on everolimus alone			X	

Chemistries & liver function tests*	X	Day 28 (+/- 7 days) while on therapy	X	
Fasting cholesterol / triglycerides*	X	Day 28 (+/- 7 days) while on therapy	X	
MRI of the brain**	X	X	X	X ±
Hepatitis B/C testing*	X			
Tissue testing for treatment selection***	X			
Translational Research:				
Archival tumor tissue	X			
Research blood draw****	X			
Survival				X ±

\*See sections 7.1.1 and 7.1.2 for lists of specific tests to be ordered at screening and during treatment, respectively

\*\*With optional MRS at baseline, end of cycles 2 and 6, and at the time of tumor progression

\*\*\* See section 7.3.2 for specific tests to be done

\*\*\*\*If sample not already available in UCSF Tissue Bank

†If patients are unable to return for an in-person visit, a phone toxicity check will be acceptable

‡Vital signs include temp, BP, heart rate, respiratory rate, and weight. Height will be done at screening only.

§At screening, “toxicity check” refers to assessment of baseline conditions

¶Please refer to protocol text (Section 7.1) for time windows for all assessments. Phone contact for survival is also acceptable as per protocol text.

§Surveys will be filled out at the end of every 6 cycles while on treatment and then at 1 year post-completion of treatment or at the time of tumor progression if sooner than 1 year post-completion of treatment

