## Glossary of terms

Assessment	A procedure used to generate data required by the study
Baseline	For efficacy evaluations, the baseline assessment will be the last available assessment before or on the date of randomization.  For safety evaluations (i.e. laboratory assessments and vital signs), the baseline assessment will be the last available assessment before or on the start date of study treatment.  The value obtained at baseline assessments, referred to as “baseline value” will be used as reference for the patient.
Control drug	A study treatment used as a comparator to reduce assessment bias, preserve blinding of investigational drug, assess internal study validity, and/or evaluate comparative effects of the investigational drug
Dose level	The dose of drug given to the patient (total daily or weekly etc.)
Enrollment	Point/time of patient entry into the study; the point at which informed consent must be obtained (i.e. prior to starting any of the procedures described in the protocol)
Investigational drug	The study treatment whose properties are being tested in the study; this definition is consistent with US CFR 21 Section 312.3 and is synonymous with “investigational new drug.”
Investigational treatment	Drug whose properties are being tested in the study as well as their associated placebo and active treatment controls (when applicable). This also includes approved drugs used outside of their indication/approved dosage, or that are tested in a fixed combination. Investigational treatment generally does not include other study treatments administered as concomitant background therapy required or allowed by the protocol when used in within approved indication/dosage
Medication number	A unique identifier on the label of each study treatment package which is linked to one of the treatment groups of a study
Other study treatment	Any drug administered to the patient as part of the required study procedures that was not included in the investigational treatment
Patient	A unique identifying number assigned to each patient/subject/healthy volunteer who enrolls in the study
Period	A subdivision of the study timeline; divides stages into smaller functional segments such as screening, baseline, titration, washout, etc.

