#### **4 Study design**

Treatment for patients with previously untreated LGG will be selected by whether or not their tumor has ATRX loss and/or 1p/19q chromosomal co-deletion. If the tumor is ATRX lost or 1p/19q intact, then patients will be further selected by whether or not their tumor demonstrates activation of the PI3K/mTOR pathway. If activation is present, patients will be treated in Arm 1 with single-agent everolimus at 10 mg daily continuously. If activation is not present, patients will be treated in Arm 2 with combined everolimus and TMZ. Everolimus will be given at 10 mg daily continuously, and TMZ will be dosed initially at 150 mg/m^2/day for 5 days out of a 28-day cycle. If ATRX is intact, 1p/19q co-deletion should be confirmed, or if only 1p/19q co-deletion is available and present, patients will be treated in Arm 3 with single-agent everolimus at 10 mg daily continuously. In all arms, treatment with everolimus will continue for up to 24 cycles, after which patients will be followed with interval MRIs until progression. In Arm 2, TMZ will be stopped after 12 cycles.

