### 5.1 Inclusion and Exclusion criteria

Patients must have baseline evaluations performed prior to the first dose of study drug and must meet all inclusion and exclusion criteria. Results of all baseline evaluations, which assure that all inclusion and exclusion criteria have been satisfied, must be reviewed by the Principal Investigator or his/her designee prior to enrollment of that patient. In addition, the patient must be thoroughly informed about all aspects of the study, including the study visit schedule and required evaluations and all regulatory requirements for informed consent. The written informed consent must be obtained from the patient prior to enrollment. The following criteria apply to all patients enrolled onto the study unless otherwise specified.

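### No follow-up MRI is tied to the 33- or 38-month landmark, so landmark PFS can be overstated, probably by about 0.5 to 1.6 points

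*Combined protocol and SAP*

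**What the plan says.** All references are to the combined protocol and SAP.

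- **Endpoint and clock.** Section 3 sets PFS at 33 months (Arms 1 and 2) and 38 months (Arm 3). Section 9.1 counts PFS from enrolment and censors event-free patients at last contact. Section 9.5.2 estimates it by Kaplan-Meier.
- **Follow-up scans.** Section 7.1.3 starts them at completion of study treatment: "every 4 months (+/- 2 weeks) for 1 year, then every 6 months (+/- 4 weeks", the second interval for two more years.
- **Completion.** Section 4 says "treatment with everolimus will continue for up to 24 cycles", and Section 7.1.2 says "A cycle will be 28 days in length regardless of treatment delays". Section 7.1.3 says "After administration of everolimus for two years, patients will have completed study treatment".
- **Enrolment.** The Glossary calls it "the point at which informed consent must be obtained". Section 5.1 says baseline results "must be reviewed by the Principal Investigator or his/her designee prior to enrollment of that patient", which places it later.
- **Off therapy.** Section 7.1.3: "Patients will be followed according to routine clinical practice after removal from protocol therapy", and "If patients are not being seen regularly in clinic, then phone calls for PFS and OS will be made every 6 months". Section 7.2.2 provides for anatomic imaging after treatment ends and until progression, without limiting it to completers.
- **Analysis time.** Section 9.5 waits until landmark PFS is known for every patient. Section 9.5.2 allows analysis once everyone has completed 33 (38) months. 'Known' is not defined.

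No section says how progression first seen on a scan is dated.

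**The concern.** Each arm's primary result is PFS at a single time, set against 50% in Section 9.3. Section 7.2 makes MRI, read with clinical evaluation, the main means of detecting progression. If a tumour grows after the last scan before the landmark, and this shows only on MRI, it is found at the next scan. Dated to that scan, the patient counts as progression-free at the landmark. The error runs one way within the trial's own estimate, and a larger sample would not remove it.

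A second route is censoring at last contact. A patient last scanned before the landmark and then only telephoned can count as progression-free at it. If progression is dated to the scan, this adds little to the sizes below, since a later scan would not change the estimate at the landmark anyway. It matters under any other dating rule, and for early stoppers followed mainly by phone.

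**Working it through.** **1. The plan's own figure.** Section 9.3 gives 35 patients per arm, 50% against 70%, a one-tailed 90% interval and 86%. Exact binomial: P(X ≥ 22 | 35, 0.50) = 0.088 and P(X ≥ 22 | 35, 0.70) = 0.865. So ≥22/35 reproduces the 86%, but this rule is inferred. The plan states no success rule.

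**2. Scan calendar** (30.4375 days per month, treatment starting at enrolment). 24 × 28 = 672 days = 22.1 months.

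| Completion | +4 | +8 | +12 | +18 |
|---|---|---|---|---|
| 22.1 (24 cycles) | 26.1 | 30.1 | 34.1 | 40.1 |
| 24 (two years) | 28 | 32 | 36 | 42 |

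The windows are ±0.46 month, and ±0.92 month for the +18 scan.

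**3. Start delay.** The documents do not fix the time from enrolment to first dose. I assume 0 to 28 days (0 to 0.92 month), borrowing the longest screening window in Section 7.1.1.

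- Month 38 then lies outside every window. The nearest edges are 36 + 0.92 + 0.46 = 37.4 and 40.08 − 0.92 = 39.2. A delay of (38 − 36) × 30.44 − 14 = 46.9 days would reach it.
- Month 33 is reached only on the two-year reading, with a delay of at least (33 − 32) × 30.44 − 14 = 16.4 days and a scan late in its window.

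**4. Size if all gap progressions are found only on scheduled scans.** Assume exponential PFS, a true landmark value of 50%, no loss to follow-up, and progression dated to the scan. Expected estimate = 0.5^(last scan ÷ landmark), at nominal dates:

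| Case | Arms 1 and 2 | Arm 3 |
|---|---|---|
| 24 cycles, no delay | 0.5^(30.08/33) = 0.532 (+3.2 points) | 0.5^(34.08/38) = 0.537 (+3.7) |
| Two years, no delay | 0.5^(32/33) = 0.511 (+1.1) | 0.5^(36/38) = 0.519 (+1.9) |
| Two years, 28-day delay | 0.501 (+0.1) | 0.510 (+1.0) |

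**5. Middle case.** Delay spread over 0 to 28 days, scans spread over their windows, half of gap progressions found clinically. By simulation: +1.3 / +1.6 points on 24 cycles and +0.5 / +0.7 on two years. As a hand check, the mean delay is 14 days (0.46 month), so on 24 cycles half of 0.5^(30.54/33) − 0.5 is 1.3 points and half of 0.5^(34.54/38) − 0.5 is 1.6.

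**6. Why a scan merely near the landmark is not enough.** On two years with a 28-day delay, the scan window runs from 32.46 to 33.38 months. About (33.38 − 33) ÷ 0.92 = 41% of those scans fall after month 33, and progression first seen on them is dated past the landmark. With all gap progressions found on scans, the Arms 1 and 2 overstatement is then +2.0 points, against +0.1 at nominal dates.

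**7. Yardstick.** Standard error = √(0.25/35) = 8.5 points.

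**8. Early stoppers.** If a 6-month gap before the landmark applied to everyone, the estimates would be 0.5^(27/33) = 0.567 and 0.5^(32/38) = 0.558 (+6.7 / +5.8 points). The figures in step 4 are therefore no ceiling for that subgroup, whose size the documents do not give.

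**The case against.** **The effect is small, and clinical detection shrinks it.** This stands. Section 7.2.3 counts definite clinical deterioration as progression, so the figures of 3.2 and 3.7 points need every gap progression to be silent until a scan. The one-half share in the middle case has no source in the documents.

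**The benchmark may carry the same lag.** This stands too. The 32.9- and 37.9-month medians in Section 9.3 come from a study that Section 1.1 calls retrospective, and its scan spacing is not given. A reader might infer that the schedule inflates false-positive error to 16.4% / 18.0%, the values of P(X ≥ 22 | 35) at 0.532 and 0.537. The documents do not support that. The success rule is inferred, the case is the worst one, and the benchmark is taken to have no lag. With an assumed 2-month benchmark lag and a 28-day start delay, 0.5^(last scan ÷ (landmark − 2)) gives 8.8% / 10.8% on 24 cycles and 5.4% / 7.2% on two years. The direction is open.

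**Section 9.5 already waits until landmark PFS is known.** This answers part of the point about patients contacted without a scan. A reader might infer that such patients will certainly be counted as progression-free, but a strict reading of Section 9.5 would prevent that. What remains is that 'known' is undefined and Section 9.5.2 permits analysis on elapsed time.

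**Early stoppers are imaged under Section 7.2.2.** They are, so it would be wrong to say that they have no imaging plan. But that section gives no post-treatment dates, and Section 7.1.3 refers patients off therapy to routine practice.

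**Conclusion.** The point holds as a modest, avoidable upward bias in the trial's own landmark estimates. No scan is tied to month 33 or 38, and dating and censoring are left open. The likely size is about 0.5 to 1.6 points; for completers at nominal dates it ranges from close to zero to 3.2 / 3.7. These figures rest on an exponential curve, a true value of 50%, dating to the scan, an assumed start delay of 0 to 28 days and, for the middle range, half of gap progressions found clinically.

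It does not show that success against 50% is favoured. Nor is it certain that no scan can fall at month 38, since that depends on the assumed limit on the start delay. The change is worth making because it is cheap and bears on the primary endpoint. The defect does not undermine the design.

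**What to change.** 1. Time the planned follow-up MRI nearest the landmark to month 33 (Arms 1 and 2) or month 38 (Arm 3) from enrolment, for every patient still progression-free, including those who stopped early. Give it a window and count its result at the nominal month (step 6 shows why). Keep later intervals no longer than the plan's.
2. State that progression found on any other scan is dated to that scan, and censor at the last adequate MRI rather than last contact.
3. In Section 9.5, define 'known' as an earlier event or a scan at or after the landmark (the landmark scan in its window qualifies). Align Section 9.5.2 with it.
4. Add an interval-censored sensitivity analysis, which also covers patients already past the landmark.
5. Reconcile 24 cycles with two years, and say which event marks enrolment. Report the scan spacing behind the historical medians, or state that it is unknown.

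**Cost.** Mostly wording. With no start delay, the nearest scans on 24 cycles come forward by 34.1 − 33 = 1.1 and 40.1 − 38 = 2.1 months, and later scans shift with them. On two years the nearest scans are at 32 and 36. Moving only those would stretch the preceding interval to 33 − 28 = 5 or 38 − 32 = 6 months, against 4 in the plan, so an earlier scan must move too or one must be added. Some early stoppers may need a scan near the landmark.

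The estimate becomes slightly less favourable. If the historical medians carry a detection lag, the comparison becomes conservative. With a 2-month lag, and the 70% target on the benchmark's scale, 0.5^(L/(L − 2)) and 0.7^(L/(L − 2)), where L is the landmark month, give under ≥22/35 an illustrative error of 5.3% / 5.7% and power of 81% / 82%, against 86.5% with no lag.
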